13.4.5.	Adverse Events of Special Interest (AESI).....	59
13.5.	Expediting Reporting Requirements for Serious Adverse Events	59
14.	STUDY ADMINISTRATION AND INVESTIGATOR OBLIGATIONS	60
14.1.	Regulatory and Ethical Compliance	60
14.2.	Enrollment.....	60
14.3.	Informed Consent.....	61
14.4.	Case Report Forms and Record Maintenance.....	61
14.5.	Publication of Study Results.....	61
14.6.	Study Discontinuation.....	62
15.	REFERENCES	64
	APPENDIX I REFERENCE SAFETY INFORMATION FOR IBRUTINIB	67
	APPENDIX II FOLLICULAR LYMPHOMA INTERNATIONAL PROGNOSTIC INDEX (FLIPI)	68

APPENDIX III ECOG PERFORMANCE SCALE.....	71
APPENDIX IV COCKCROFT- GAULT FORMULA FOR ESTIMATED CREATININE CLEARANCE	71
APPENDIX V MEDICATION CALENDAR	72
APPENDIX VI DRUGS TO BE AVOIDED OR USED WITH CAUTION.....	74
APPENDIX VII LUGANO REVISED RESPONSE CRITERIA FOR NON-HODGKIN LYMPHOMA ³²	75
APPENDIX VIII RECOMMENDATIONS FOR INITIAL MANAGEMENT OF ELECTROLYTE ABNORMALITIES AND PREVENTION OF TUMOR LYSIS SYNDROME	77
APPENDIX IX DEFINITIONS OF LABORATORY AND CLINICAL TUMOR LYSIS SYNDROME	79
APPENDIX X CHILDS PUGH CLASSIFICATION.....	80
APPENDIX XI IBRUTINIB PK SAMPLE COLLECTION.....	81
APPENDIX XII CORRELATIVE STUDY SAMPLE SUBMISSION.....	83

SYNOPSIS

Study Title:	Ibrutinib and Venetoclax in Relapsed and Refractory Follicular Lymphoma																
Protocol Number:	2016-0014																
Study Phase:	1b/2																
Study Duration:	24 months																
Objectives:	
Phase I study:
 
Primary Objective: To determine the recommended phase II doses of ibrutinib and venetoclax when combined in relapsed and refractory follicular lymphoma
 
Secondary Objective: To determine the pharmacokinetics of ibrutinib and venetoclax when dosed in combination in relapsed and refractory follicular lymphoma
 
Phase II study:
 
Primary Objective: To determine the efficacy of ibrutinib and venetoclax when combined in relapsed and refractory follicular lymphoma
 
Secondary Objective: To determine the safety and tolerability of ibrutinib and venetoclax when combined in relapsed and refractory follicular lymphoma
																
Study Design:	This is a phase I/II study in which patients will be enrolled in a standard 3+3 design. Once the maximum tolerated dose is determined, there will be a 17-patient phase II study using Simon's Minimax 2-stage design.																

Inclusion Criteria:
 
Refer to Section 4.0 for the complete and detailed list of inclusion/exclusion criteria.
	
 • Relapsed or refractory, histologically confirmed grade 1-3a follicular lymphoma which requires therapy • Must have received at least one prior systemic therapy • All risk by FLIPI 0-5 factors • No prior BTK inhibitor or BCL-2 inhibitor • ECOG performance status of ≤ 2 
  
 Required Initial Lab Values	
   
 ANC	$\geq 1000/\mu\text{L}^*$	
 
 Hemoglobin	$\geq 8.0 \text{ g/dL}^*$	
 
 Platelet count	$\geq 50,000/\mu\text{L}^*$	
 
 AST and ALT	$\leq 2.5 \times \text{ULN}^*$	
 
 Total bilirubin	$\leq 1.5 \times \text{ULN}^*, **$	
 
 CrCl	$\geq 50 \text{ mL/min}^{***}$	
 
 PT/INR and PTT (aPTT)	$< 1.5 \times \text{ULN}$	
  
 
*Unless attributable to disease, See Section 3 **Unless attributable to Gilbert's syndrome ***Use of Cockcroft-Gault actual weight
	Required Initial Lab Values		ANC	$\geq 1000/\mu\text{L}^*$	Hemoglobin	$\geq 8.0 \text{ g/dL}^*$	Platelet count	$\geq 50,000/\mu\text{L}^*$	AST and ALT	$\leq 2.5 \times \text{ULN}^*$	Total bilirubin	$\leq 1.5 \times \text{ULN}^*, **$	CrCl	$\geq 50 \text{ mL/min}^{***}$	PT/INR and PTT (aPTT)	$< 1.5 \times \text{ULN}$
Required Initial Lab Values																	
ANC	$\geq 1000/\mu\text{L}^*$																
Hemoglobin	$\geq 8.0 \text{ g/dL}^*$																
Platelet count	$\geq 50,000/\mu\text{L}^*$																
AST and ALT	$\leq 2.5 \times \text{ULN}^*$																
Total bilirubin	$\leq 1.5 \times \text{ULN}^*, **$																
CrCl	$\geq 50 \text{ mL/min}^{***}$																
PT/INR and PTT (aPTT)	$< 1.5 \times \text{ULN}$																
Exclusion Criteria:	
 • Chemotherapy, monoclonal antibody, or small molecule inhibitor ≤ 21 days prior to first administration of study treatment 																

	
• Concurrent systemic immunosuppressant therapy \leq 4 weeks of the first dose of study drug (e.g. cyclosporine A, tacrolimus, etc. or chronic administration of $>$ 20 mg day of prednisone or equivalent)• Known allergy to xanthine oxidase inhibitors and/or rasburicase for subjects at risk for tumor lysis syndrome• Infection requiring systemic treatment that was completed \leq14 days• Significant unresolved toxicities from prior anti-cancer therapy• Known bleeding disorders (e.g. von Willebrand's disease) or hemophilia.• History of stroke or intracranial hemorrhage within 6 months• Known history of HIV• Active hepatitis C or hepatitis B infection. Subjects who are positive for hepatitis B core antibody, hepatitis B surface antigen, or hepatitis C antibody must have a negative polymerase chain reaction (PCR) result before enrollment. Those who are PCR positive will be excluded.• Subjects with chronic liver disease with hepatic impairment Child-Pugh class B or C (See Appendix X)• Major surgery within 4 weeks of first dose of study drug.• Concomitant use of warfarin or other Vitamin K antagonists.• Subjects who received a strong cytochrome P450 (CYP) 3A inhibitor within 7 days prior to the first dose of ibrutinib or subjects who require continuous treatment with a strong CYP3A inhibitor (See Appendix VI)• Lactating or pregnant.• Current or history of graft versus host disease
--	---

Study Treatment:	
Phase I study:
 
Three patients will be enrolled at Dose Level 0 (DL0): Ibrutinib 420 mg daily and Venetoclax 400 mg daily. Each cycle is 28-days. Patients will be monitored for dose limiting toxicity (DLT) during Cycle 1. Patients will receive the combination until progression or unacceptable toxicity. Patients will be followed throughout the duration of therapy through progression until next line of therapy.
 
Dose Levels
 
  
 Dose Level	Ibrutinib	Venetoclax	
   
 0	420 mg	400 mg	
 
 1	560 mg	400 mg	
 
 2	560 mg	600 mg	
  
 
Phase II study:
 
Patients will be enrolled at the recommended phase II dose. Duration of therapy will depend on depth of response. Patients who achieve a complete remission may discontinue therapy after 24 cycles. These patients must undergo a PET-CT during Cycle 24 to confirm they are still in a complete remission prior to discontinuation. Patients who achieve a partial response will continue therapy until progression or unacceptable toxicity. Patients will be followed throughout the duration of therapy through progression until next line of therapy. Patients who achieve a complete remission and discontinue therapy after 24 cycles will be monitored closely with serial imaging and may be reinitiated on treatment within one year of discontinuation for either progression of disease or at the discretion of the treating physician.
	Dose Level	Ibrutinib	Venetoclax	0	420 mg	400 mg	1	560 mg	400 mg	2	560 mg	600 mg
Dose Level	Ibrutinib	Venetoclax											
0	420 mg	400 mg											
1	560 mg	400 mg											
2	560 mg	600 mg											
Participating Centers:	
MedStar Georgetown University Hospital Hackensack University Medical Center Seattle Cancer Care Alliance
												

ABBREVIATIONS

AE	Adverse event
AESI	Adverse events of special interest
ALT	Alanine transaminase
AML	Acute myeloid leukemia
AST	Aspartate transaminase
AUC	Area under the curve
BCR	B-cell receptor
BTK	Bruton-tyrosine kinase
CDUS	Clinical data update system

CI	Confidence interval
CLL	Chronic lymphocytic leukemia
C _{max}	Peak concentration
CR	Complete response
CRF	Case report form
CTCAE	NCI Common Terminology Criteria for Adverse Events
DCF	Data clarification form
DLBCL	Diffuse large B-cell lymphoma
DLT	Dose limiting toxicity
DMC	Data Monitoring Committee
DMSO	Dimethyl sulfoxide
DSM-IV	Diagnostic and Statistical Manual of Mental Disorders (4th edition)
ECG	Electrocardiogram
ECOG	Eastern Cooperative Oncology Group
EDC	Electronic data capture
FCBP	Female of childbearing potential
FL	Follicular lymphoma
GCP	Good Clinical Practice
GELF	Groupe d'Etude des Lymphomes Folliculaires
HBsAg	Hepatitis B surface antigen
HBV	Hepatitis B virus
HCV	Hepatitis C virus
HDPE	High-density polyethylene
HIV	human immunodeficiency virus
IAC	Interim Analysis Committee
IB	Investigator's Brochure
ICF	Informed Consent Form
ICH	International Conference on Harmonisation
IEC	Independent Ethics Committee
IRB	Institutional Review Board
IVF	Intravenous fluids
IVRS	Interactive voice response system
IWRS	Interactive web response system
LC-MS/MS	Liquid chromatography/mass spectrometry/mass spectrometry
LDH	Lactate dehydrogenase
MCL	Mantle cell lymphoma
MedDRA	Medical Dictionary for Regulatory Activities
MM	Multiple myeloma

MRU	Medical Resource Utilization
MTD	Maximal tolerated dose
NCCN	National Comprehensive Cancer Network
NGS	Next-Generation Sequencing
NHL	Non-Hodgkin lymphoma
ORR	Overall response rate
OS	Overall survival
PCR	Polymerase chain reaction
PD	Pharmacodynamic
PFS	Progression-free survival
P-gp	P-glycoprotein
PK	Pharmacokinetic
PML	Progressive multifocal leukoencephalopathy
PQC	Product Quality Complaint
PR	Partial response
PRO	patient-reported outcome(s)
QD	Daily
SAE	Serious adverse event
SD	Stable disease
SJS	Stevens-Johnson Syndrome
TEAE	Treatment-emergent adverse event
TLS	Tumor lysis syndrome
Tmax	Time to reach maximum concentration
Vd	Volume of distribution
Vss	Volume of distribution at steady state
USP	United States Pharmacopeia

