3.2. Exclusion Criteria

To be enrolled in the study, potential subjects must meet NONE of the following exclusion criteria:

1. Chemotherapy, monoclonal antibody, or small molecule kinase inhibitor ≤ 21 days prior to first administration of study treatment
2. Prior exposure to a BTK or BCL-2 inhibitor.
3. History of allergic reactions attributed to compounds of similar chemical or biologic composition to ibrutinib or venetoclax.
4. Known allergy to xanthine oxidase inhibitors and/or rasburicase for subjects at risk for tumor lysis syndrome.
5. History of other malignancies, except:
 - Malignancy treated with curative intent and with no known active disease present for ≥ 3 years before the first dose of study drug and felt to be at low risk for recurrence by treating physician.
 - Adequately treated non-melanoma skin cancer or lentigo maligna without evidence of disease.
 - Adequately treated carcinoma in situ without evidence of disease.

6. Concurrent systemic immunosuppressant therapy (e.g., cyclosporine A, tacrolimus, etc., or chronic administration [>14 days] of > 20 mg/day of prednisone) within 28 days of the first dose of study drug.
7. Undergone an allogeneic stem cell transplant within the past 1 year.
8. Current or history of graft versus host disease
9. Vaccinated with live, attenuated vaccines within 4 weeks of first dose of study drug.
10. Recent infection requiring systemic treatment that was completed ≤ 14 days before the first dose of study drug.
11. Unresolved toxicities from prior anti-cancer therapy, defined as having not resolved to Common Terminology Criteria for Adverse Event (CTCAE, version 4.03), grade ≤ 1 , or to the levels dictated in the inclusion/exclusion criteria with the exception of alopecia.
12. Known bleeding disorders (e.g., von Willebrand's disease) or hemophilia.
13. History of stroke or intracranial hemorrhage within 6 months prior to enrollment.
14. Known HIV infection
15. Active infection with hepatitis C virus (HCV) or hepatitis B virus (HBV).
 - Subjects who are positive for hepatitis B core antibody, hepatitis B surface antigen, hepatitis C antibody, must have a negative polymerase chain reaction (PCR) result for the respective disease before enrollment. Those who are PCR positive will be excluded.
16. Any uncontrolled active systemic infection.
17. Major surgery within 4 weeks of first dose of study drug.

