18. Any life-threatening illness, medical condition, or organ system dysfunction that, in the investigator's opinion, could compromise the subject's safety or put the study outcomes at undue risk.
19. Currently active, clinically significant cardiovascular disease, such as uncontrolled arrhythmia or Class 3 or 4 congestive heart failure as defined by the New York Heart Association Functional Classification; or a history of myocardial infarction, unstable angina, or acute coronary syndrome within 6 months prior to randomization.
20. Unable to swallow capsules or tablets or malabsorption syndrome, disease significantly affecting gastrointestinal function, or resection of the stomach or small bowel, symptomatic inflammatory bowel disease or ulcerative colitis, or partial or complete bowel obstruction.
21. Concomitant use of warfarin or other Vitamin K antagonists.
22. Subjects who received a strong cytochrome P450 (CYP) 3A inhibitor within 7 days prior to the first dose of ibrutinib or subjects who require continuous treatment with a strong CYP3A inhibitor (See Appendix VI)
23. High-grade transformation confirmed by biopsy.
24. Malabsorption syndrome or other condition precluding enteral route of administration.
25. Known CNS involvement by lymphoma

26. Erythema multiforme, toxic epidermal necrolysis, or Stevens-Johnson syndrome
27. Lactating or pregnant.
28. Unwilling or unable to participate in all required study evaluations and procedures.
29. Unable to understand the purpose and risks of the study and to provide a signed and dated informed consent form (ICF) and authorization to use protected health information (in accordance with national and local subject privacy regulations).
30. Currently active, clinically significant hepatic impairment (\geq moderate hepatic impairment according to the Child Pugh classification (class B or C)) (see Appendix X)

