4. REQUIRED DATA

4.1. Screening Phase

To be completed within 14 DAYS before Cycle 1 Day 1:

- All blood work

To be completed within 28 DAYS before Cycle 1 Day 1

- Any radiologic study (e.g., PET, CT, or MRI) that is utilized for tumor measurement
- History and physical

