7. CONCOMITANT MEDICATIONS/PROCEDURES

7.1. Permitted Concomitant Medications

Supportive medications in accordance with standard practice (such as for emesis, diarrhea, etc.) are permitted. Use of neutrophil growth factors (filgrastim and pegfilgrastim) or red blood cell growth factors (erythropoietin) is permitted while on therapy per institutional policy and in accordance with the ASCO guidelines. [31] Transfusions may be given in accordance with institutional policy.

Short courses (≤ 14 days) of steroid treatment for non-cancer related medical reasons (e.g., joint inflammation, asthma exacerbation, rash, antiemetic use and infusion reactions) at doses that do not exceed 100mg per day of prednisone or equivalent are permitted.

If clinically indicated, antimicrobial prophylaxis can be considered. Consider drug-drug interactions before initiating an agent. (Appendix V) Although there is a potential for drug-drug interactions, there is likely to be limited potential clinical effects, therefore Bactrim

(trimethoprim sulfamethoxazole) can be considered for Pneumocystis prophylaxis, with close clinical monitoring.

After consultation with the investigator the following may be considered; localized hormonal or bone sparing treatment for non-B-cell malignancies, and localized radiotherapy for medical conditions other than the underlying B-cell malignancies.

The following may be considered: localized hormonal or bone sparing treatment for non-B-cell malignancies, and localized radiotherapy for medical conditions other than the underlying B-cell malignancies.

Treatment for autoimmune cytopenias are permitted for <14 days at doses that do not exceed 100 mg per day of prednisone or equivalent.

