7.3. Prohibited Concomitant Medications

Any chemotherapy, anticancer immunotherapy, experimental therapy, or radiotherapy is prohibited while the subject is receiving ibrutinib treatment.

Corticosteroids for the treatment of the underlying disease are prohibited. Corticosteroids for the treatment of non-cancer related reasons for longer than 14 days and/or at doses >100mg of prednisone or its equivalent are prohibited.

Due to drug-drug interactions, strong CYP3A inhibitors and inducers should not be administered with venetoclax or ibrutinib. (See Appendix V).

Live-virus vaccines should not be given within 28 days prior to the initiation of study treatment, at any time during study treatment, or in the 30 days following last dose of study treatment.

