11.2. Withdrawal from Study Treatment

Each subject has the right to withdraw from the study at any time. In addition, the investigator will discontinue a subject from the study at any time if the investigator considers it necessary for any reason including:

- The investigator believes it is in the best interest of the subject;
- The subject's response to therapy is unsatisfactory, as evidenced by progression of disease while on study drug;
- The subject requires radiotherapy, cancer-related surgery as a result of tumor progression, or alternate anti-neoplastic agents during the study period;
- Noncompliance with the protocol;
- Unacceptable adverse event(s), or
- General or specific changes in the patient's condition render the patient unacceptable for further treatment in the judgment of the investigator.

If, at any time the constraints of this protocol are detrimental to the patient's health and/or patient no longer wishes to continue protocol therapy, protocol therapy shall be discontinued. In this event:

- Notify the Study Chair
- Document the reason(s) for discontinuation of therapy in the study record.
- Follow the patient for relapse, progression, survival, and secondary malignancies or new primaries.

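### Long-term prednisone at 20 mg/day or less is allowed at entry but barred on study after 14 days, with no provision for a stable or replacement dose

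*Combined protocol and SAP*

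**What the plan says.** Entry. The Synopsis, under Exclusion Criteria, sets the steroid limit at chronic use above "20 mg day of prednisone or equivalent" within 4 weeks of first dose, and does not say how many days count as chronic. Section 3.2, exclusion 6, supplies the duration: "chronic administration [>14 days] of > 20 mg/day of prednisone", within 28 days of first dose.

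On study. Section 7.3 states: "Corticosteroids for the treatment of non-cancer related reasons for longer than 14 days and/or at doses >100mg of prednisone or its equivalent are prohibited". Section 7.1 has two steroid allowances, both time-limited and both capped at 100 mg per day of prednisone or equivalent. One covers courses of up to 14 days "of steroid treatment for non-cancer related medical reasons". The other reads: "Treatment for autoimmune cytopenias are permitted for <14 days".

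Appendix VI. The prohibited list names steroids only when given with anti-neoplastic intent. Glucocorticoids such as prednisone appear separately, among the weak CYP3A inducers to be used with caution, with no dose or duration.

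Discretion. Exclusion 18 lets the investigator keep out a patient whose condition could compromise safety or "put the study outcomes at undue risk". Section 11.2 says protocol therapy is to be discontinued if "the constraints of this protocol are detrimental" to the patient's health.

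**The concern.** The entry rule tests dose and duration together. The on-study rule can be triggered by duration alone. A patient on low-dose maintenance prednisone for a non-cancer condition therefore passes the steroid criterion and, if the drug continues, breaches 7.3 during treatment. Elsewhere the protocol does match entry to conduct: warfarin is both an exclusion and a prohibited drug, and live vaccines are barred before and during treatment.

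At stake are individual safety and compliance. A patient who stops a maintenance steroid risks withdrawal effects or a flare of the treated condition. A patient on adrenal replacement cannot safely stop at all. A site that reads only Appendix VI may conclude that maintenance prednisone is acceptable with caution, while a site that reads 7.3 will conclude the opposite. With three participating centers, the same patient could be handled differently.

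**Working it through.** There is no plan figure to reproduce and no arithmetic to run. The check sets the rules side by side for steroids given for a non-cancer reason.

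- Entry test (exclusion 6): excluded if duration is more than 14 days **and** dose is above 20 mg/day.
- On-study test (7.3): prohibited if duration is more than 14 days **or** dose is above 100 mg.
- On-study allowance (7.1): at most 14 days (less than 14 for autoimmune cytopenias) and at most 100 mg/day.

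| Prednisone use | Entry | On study if continued unchanged |
|---|---|---|
| 20 mg/day or less, 14 days or less in total | eligible | permitted as a short course |
| 20 mg/day or less, more than 14 days | eligible | prohibited by 7.3 |
| above 20 mg/day, more than 14 days | excluded | prohibited by 7.3 |

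Only the middle row is misaligned. It covers every chronic dose above 0 and up to 20 mg/day; 10 mg/day is an ordinary example.

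Four readings could remove the mismatch.

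1. Reading the and/or in 7.3 as a plain *and*. That would permit any duration up to 100 mg/day, which does not fit the 14-day limit in 7.1.
2. Treating the prednisone clause in exclusion 6 as one example of immunosuppression, so that lower doses might also exclude. A stated dose threshold would then serve no purpose, and the Synopsis repeats it.
3. Treating the Appendix VI caution listing as permission. It sets no dose or duration and does not refer to 7.3, so it does not override the explicit prohibition.
4. Finding an exemption or a taper instruction elsewhere. Neither is present. Section 4.1 places the history and physical under "To be completed within 28 DAYS before Cycle 1 Day 1", so the site should learn of the steroid before dosing, but nothing says what to do about it.

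Compliant routes remain: complete a taper before Cycle 1 Day 1, delay Day 1 to allow one, or screen the patient out under exclusion 18. None of them keeps on study a patient who needs the steroid to continue.

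**The case against.** The strongest reply is that this is a gap between two rules with different jobs. Exclusion 6 is a pre-dose immunosuppression window, while 7.3 governs conduct on treatment. Entry criteria need not restate every on-study prohibition, and a patient can meet the first rule and then be asked to meet the second. That stands: a reader might infer that the protocol contradicts itself, and strictly it does not.

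A reader might also infer that an enrolled patient on maintenance steroid must be taken off study treatment or have the steroid stopped abruptly. The documents do not support that either. Section 7.3 attaches no discontinuation rule, removal for noncompliance under 11.2 is left to the investigator's judgment, and nothing directs abrupt withdrawal.

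The adrenal-replacement patient is also hypothetical: the documents describe no such patient and give no count, and in a 17-patient phase II there may be none.

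What the reply does not remove is that a patient who needs the steroid can comply with 7.3 only by stopping it. Exclusion 18 is discretionary, does not mention steroids, and does not naturally reach a well patient on a stable low dose. Leaving the matter to 11.2 means enrolling someone whose known maintenance drug already conflicts with the protocol.

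**Conclusion.** The mismatch holds on the plain wording of exclusion 6 and 7.3, and it is minor. It is a foreseeable compliance and safety problem for an unknown, probably small number of patients. The conclusion assumes that the and/or in 7.3 means either condition suffices and that the 20 mg/day threshold defines the steroid limit at entry.

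It should not be stretched to the trial's results. A reader might infer distorted dose-limiting toxicity counts, but section 5.2.1 shows that escalation has largely been completed, with Dose Level 3 closed. A reader might infer a biased toxicity summary, but section 12.3 summarizes toxicity with attribution. The Simon design in section 12.2 (at least 3 responders among 10 to continue, at least 9 among 17 to accept) does not depend on the steroid rules.

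**What to change.** Preferred: add one sentence to each of 7.1 and 7.3. A stable dose of 20 mg/day or less of prednisone or equivalent, started before enrollment for a non-cancer indication, may continue without increase, as may physiological adrenal replacement whenever started. The 14-day and 100 mg limits then apply to new or increased systemic courses. The word systemic also keeps inhaled and topical use outside a prohibition that at present names corticosteroids without qualification. Record the dose as a concomitant medication, and add a cross-reference to 7.3 in Appendix VI.

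Cost: wording only. Table 1 already collects medication history before Cycle 1 and at treatment visits, so no procedure is added. The downsides are a possible small steroid contribution to response and weak CYP3A induction, for which section 7.2.1 already asks for caution with venetoclax.

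Acceptable alternative: amend the Synopsis and exclusion 6 to exclude patients who need systemic corticosteroids for more than 14 days on study, and state that a taper completed before Cycle 1 Day 1 preserves eligibility. This avoids continued steroid exposure at the cost of slightly narrower eligibility. On its own it does not cover replacement first needed after enrollment.
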